3.2.3 Secondary outcome variables

The secondary outcome variables which address the further efficacy of AZD2811 are described in Section 9.4.2.2 of the CSP. PK concentrations are secondary outcome variables as well.

Safety and tolerability will be evaluated in terms of AEs, vital signs, physical examination, clinical chemistry, TSH, prothrombin time/PTT/INR (coagulation is included in laboratory), hematology, ECG, and urinalysis, as well as infusion interruptions, cycle delays, dose reductions, and dose discontinuations.

Due to the decision to terminate enrolment prior to completion and the limited number of patients who received AZD2811+durvalumab, the efficacy analysis will be reduced to listings and only the outcomes listed in the following sub-sections will be derived.

3.2.3.1 Overall survival (OS)

Overall survival is defined as the time from the date of first dose of study intervention in the induction phase until death due to any cause regardless of whether the subject withdraws from study therapy or receives another anti-cancer therapy (i.e. date of death or censoring – date of first dose + 1).

Any subject not known to have died at the time of analysis will be censored based on the last recorded date on which the subject was known to be alive (SUR_DAT, recorded within the SURVIVE module of the eCRF).

Note: Survival calls will be made in the week following the date of DCO for the analysis, and if subjects are confirmed to be alive or if the death date is post the DCO date these subjects will be censored at the date of DCO.

The status of ongoing, withdrawn (from the study) and “lost to follow-up” subjects at the time of the final OS analysis should be obtained by the site personnel by checking the subject’s notes, hospital records, contacting the subject’s general practitioner and checking publicly-available death registries. In the event that the subject has actively withdrawn consent to the processing of their personal data, the vital status of the subject can be obtained by site personnel from publicly available resources where it is possible to do so under applicable local laws.

3.2.3.2 Best objective response (BOR)

Best objective response (BOR) is calculated based on the overall visit responses from each RECIST assessment, described in Section 3.1.6.3. It is the best response a subject has had following first administration of study intervention but prior to starting any subsequent cancer therapy and up to subsequently confirmed RECIST progression or the last evaluable assessment in the absence of RECIST progression. Categorization of BOR will be based on RECIST using the following response categories: CR, PR, SD, PD and NE.

For determination of a best response of SD, the earliest of the dates contributing towards a particular overall visit assessment will be used. SD should be recorded at least 6 weeks minus 1 week, i.e. at least 35 days (to allow for an early assessment within the assessment window), after first administration of study intervention.

BOR will be determined programmatically based on RECIST using all site investigator data up until the first progression event (i.e. progression or death). For subjects whose progression event is death, BOR will be calculated based upon all evaluable RECIST assessments prior to death. In addition, only the RECIST assessments prior to start of subsequent cancer therapy (note that for this analysis, palliative or adjuvant radiotherapy is not considered a subsequent anticancer therapy) will be included.

For subjects who die with no evaluable RECIST assessments, if the death occurs \leq 13 weeks (i.e. 12 weeks + 1 week to allow for a late assessment within the assessment window) after first dose study intervention, then BOR will be assigned to the progression (PD) category. For subjects who die with no evaluable RECIST assessments, if the death occurs $>$ 13 weeks after start of first dose of study intervention then BOR will be assigned to the NE category.

3.2.3.3 Pharmacokinetics

Whole blood samples will be collected for measurement of whole blood concentrations of AZD2811 and its metabolite (AZ12102238). Serum samples will be collected for measurement of serum concentrations of durvalumab.

Concentrations below the lower limit of quantification will be reported in the following way:

1. Individual BLQ concentrations are reported as NQ (not quantifiable).
2. For summary data:
 - a. If, at a given time point, 50% or less of the concentrations are NQ, the geometric mean, geometric CV, geometric standard deviation, arithmetic mean and standard deviation are calculated by substituting the LLOQ for values which are NQ.
 - b. If more than 50%, but not all, of the concentrations are NQ, the geometric mean, geometric CV, geometric standard deviation, arithmetic mean and standard deviation are reported as not calculable (NC). The maximum value is reported from the individual data, and the minimum and median are set as NQ.
 - c. If all the concentrations are NQ, the geometric mean and arithmetic mean are reported as NQ and the geometric CV, geometric standard deviation and standard deviation as NC.
 - d. The number of values below LLOQ are reported for each time point along with the total number of collected values.
 - e. Any concentration record that is reported as not collected or not reported will be regarded as missing and excluded from summary tables and any corresponding figures.

Three values >LLOQ are required as a minimum for a concentration to be summarized. Two values are presented as a minimum and maximum with the other summary statistics as NC. The LLOQ will be reported in the CSR and in PK tables, figures and listings.

Individual concentration data may be excluded from summary tables and graphical presentation for legitimate scientific reasons. Any exclusions will be provided to programming in accordance with AZ Best Practice Guideline for the Study Level Process for Pharmacokinetic Data Analysis v2.0. Any exclusions, together with justification for the exclusion, will be clearly documented in the abbreviated CSR. These individual data will still be presented in the listings, but will be flagged to identify that they are excluded from summary outputs.

3.2.3.4 Adverse Events

An adverse event (AE) is the development of any untoward medical occurrence in a subject or clinical study participant administered a medicinal product and which does not necessarily have a causal relationship with this treatment. The full definition of AEs and serious AEs (SAEs) can be found in the CSP Appendix B.

AEs and SAEs will be collected throughout the study, from date of informed consent until 90 days after the last dose of study intervention. Events will be defined as treatment emergent if they started after dosing or prior to dosing and worsen following study intervention. AEs which start in induction phase and subsequently worsen in maintenance phase will be defined as treatment emergent for both phases. AEs which start in induction phase and are ongoing, but not worsened, in maintenance phase, will be presented for induction phase only. For dosing days, AE start timing will be collected as well to identify pre- or post-dose AEs. AEs which start on Cycle 1 Day 1 but with start time before dosing are not considered treatment emergent. AEs which start/worsen on CCI [REDACTED] but with start time before dosing are considered as treatment emergent for induction phase only as long as they do not worsen in maintenance phase afterwards.

AEs with start or worsening date in safety follow-up period (within 90 days after the last dose of study intervention) will be presented along with AEs occurring in the phase from which the subject discontinued.

A flag will be created to indicate AEs which occur within the 90 days safety follow-up period but after initiation of the first subsequent therapy following discontinuation of study intervention.

The Medical Dictionary for Regulatory Activities (MedDRA) (using the latest or current MedDRA version) will be used to code the AEs. AEs will be graded according to the National Cancer Institute Common Terminology Criteria for AEs (CTCAE Version 5.0).

Maximum CTCAE grades on treatment overall and by phase will be derived.

For durvalumab, AEs of special interest (AESI) are defined in [CSP](#) Section 8.3.12.2. Preferred terms (PT) of AESIs and adverse events of potential interest (AEPI) are detailed in the AstraZeneca durvalumab AESI/AEPI PTs list. The PTs list (current or latest version at the time of reporting) will be used to identify and distinguish AESIs and AEPIs. The AESIs and AEPIs will also be classified as immune-mediated AEs (imAE) or not imAEs. Further details are provided in an imAE Charter.

If, during the course of the study, AEs will be defined as of special interest for AZD2811, then they will be analyzed in a similar manner as AESI for durvalumab.

3.2.3.5 Laboratory Data

The laboratory variables to be measured are presented in Section 8.2.4 of the [CSP](#): Table 17 (clinical chemistry), Table 18 (hematology), Table 19 (urinalysis), and Table 20 (other safety tests, including coagulation).

White blood cell (WBC) differential counts will be presented as a percentage (relative numbers of each type of WBC in relationship to the total WBC) and as an absolute value (percentage x total WBC).

If the absolute count for a particular type of blood cell (basophils, eosinophils, lymphocytes, neutrophils, monocytes and reticulocytes) is not reported, it will be derived as the total white blood cell count multiplied by the differential percentage for that cell type.

Laboratory variables will be followed-up until end of treatment visit. Data collected during safety follow-up will be presented along with data collected during the period from which the subject discontinued.

Change from baseline in hematology and clinical chemistry will be calculated for a subset of parameters at each post-dose visit, see section 3.1.2. The subset will include the following parameters:

- Hematology
 - Haemoglobin
 - WBC
 - ANC
 - Platelets
- Clinical chemistry
 - Albumin
 - Creatinine
 - Creatinine clearance
 - Total bilirubin

- AST
- ALT
- Amylase
- Lipase
- Coagulation
 - International Ratio (INR)
 - Fibrinogen

CTC grade will be calculated at each visit. Maximum post-baseline CTC by study phase and overall will also be calculated. Clinically important changes are defined as CTCAE grade ≥ 2 or changes to CTCAE grade 3 or 4 and will be derived by study phase and overall. End of treatment results will be those which are assessed on the latest nominal visit prior or on the date subjects discontinue or complete study intervention. Absolute values will be compared to the local laboratory reference range and classified as low (below range), normal (within range or on limits of range) and high (above range). All values classified as high or low will be flagged on the listings.

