^d Magnesium required at screening and Cycle 1 Day 1, and then should be performed only as clinically indicated or per local practice.

^e Not required at all time points; refer to the Schedule of Activities tables in Section 1.3

AE = Adverse event; ALT = Alanine aminotransferase; AST = Aspartate aminotransferase; T₃ = Triiodothyronine; T₄ = Thyroxine; TSH = Thyroid-stimulating hormone.

Table 18 Hematology

Full White Blood Cell Count Differential: Neutrophils, Lymphocytes, Monocytes, Eosinophils, Basophils ^a	Red Blood Cells
	Hematocrit
Hemoglobin	Platelet count
HbA1c (baseline only)	Total white cell count
Reticulocytes ^a	

^a Can be recorded as absolute counts or as percentages. Absolute counts will be calculated by data management if entered as percentage. Total white cell count therefore has to be provided.

Table 19 Urinalysis

Bilirubin	Ketones
Blood	pH
Color and appearance	Protein
Glucose	Specific gravity

Note: Microscopy should be used as appropriate to investigate white blood cells and use the high-power field for red blood cells.

Table 20 Other Safety Tests

Coagulation Tests: prothrombin time, partial prothrombin time, international normalized ratio, fibrinogen.
HbsAg, hepatitis C antibodies, and HIV antibodies
Tuberculosis test is required at screening; method of testing will be according to Institutional Guidelines
Pregnancy test: Women of Childbearing Potential Only; serum is required at screening and within 3 days of Cycle 1 Day 1; urine may be used at future visits. Pregnancy testing will be performed monthly (28 +/- 7 days) through 90 days post last dose or until a new treatment is initiated, whichever is shorter.

If a participant shows an AST or ALT $\geq 3 \times$ ULN together with TBL $\geq 2 \times$ ULN, refer to Appendix E for further instructions on cases of increases in liver biochemistry and evaluation of HL. These cases should be reported as SAEs if, after evaluation, they meet the criteria for a Hy's law case or if any of the individual liver test parameters fulfill any of the SAE criteria. All participants meeting the criteria for HL should have further chemistry profiles performed at 28 days (± 3 days), 2 months (± 1 week), and 3 months (± 1 week) after permanent discontinuation of IP (see Appendix E).

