4.2.3.3 Laboratory

Clinical chemistry, coagulation and hematology results and change from baseline will be summarized using descriptive statistics (number of observations, mean, standard deviation, minimum, lower quartile, median, upper quartile and maximum) at each scheduled assessment time for continuous laboratory assessments). For a subset of laboratory variables (see Section 3.2.3.5) included in the current version of CTCAE, the CTCAE grade change from baseline to maximum on treatment will be summarized by phase. Urinalysis results will be listed only.

Number and percentages of clinically important changes will be presented by clinical chemistry, coagulation and hematology parameter.

Proportions of subjects with elevated liver test (elevated alanine aminotransferase (ALT) or aspartate aminotransferase (AST) (≥ 3 ULN), and elevated Total bilirubin ($\geq 2x$ ULN)) will be summarized and individual subject data for subjects with potential Hy's law will be provided.

Key subject information will be also provided for subjects with treatment-emergent clinical chemistry, coagulation or hematology values outside predefined criteria.

Plots for ALT and AST versus total bilirubin, expressed as multiples of upper limit of normal (ULN) and liver biochemistry test results over time will be created. The reference lines are 3x ULN for ALT, AST, and 2x ULN for Total bilirubin. In each plot, total bilirubin will be in the vertical axis.

Laboratory reference ranges as well as all individual laboratory data will be listed. Liver assessments, liver risk factors and liver signs and symptoms for all potential Hy's law cases will be listed separately.

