TFL number	Title	Template	Abbreviated CSR
Table 14.3.2.11	Number of subjects with adverse events leading to dose reduction of study interventions by system organ class and preferred term (Safety)	S22	X
Table 14.3.2.12	Number of subjects with adverse events leading to dose interruption of study interventions by system organ class and preferred term (Safety)	S22	X
Table 14.3.2.13	Number of subjects with adverse events leading to dose modification of study interventions by system organ class and preferred term (Safety)	S22	X
Table 14.3.3.1.1	All Deaths (Safety)	TDT010	X
Table 14.3.3.1.2	Number of subjects with adverse events with outcome of death, by system organ class and preferred term (Safety)	S13(i)	X
Table 14.3.3.2	Listing of deaths (Enrolled)	TDT040	X
Table 14.3.3.3	Adverse events with outcomes of death – key subject information (Safety)	S14	X
Table 14.3.4.1.1	Number of subjects with serious adverse events, by system organ class and preferred term (Safety)	S17(i)	X
Table 14.3.4.1.2	Number of serious adverse events, by system organ class and preferred term (Safety)	S16(ii)	X
Table 14.3.4.1.3	Number of subjects with serious adverse events, judged by investigator as possibly related to study interventions (Safety)	S17(ii)	X

TFL number	Title	Template	Abbreviated CSR
Table 14.3.4.2	Serious adverse events - Listing of key information for SAEs (Safety)	TAE180	X
Table 14.3.5.1	Number of subjects with adverse events leading to discontinuation of study intervention, by system organ class and preferred term (Safety)	S19(i)	X
Table 14.3.5.2	Adverse events leading to discontinuation of study interventions – key subject information (Safety)	TAE210	X
Table 14.3.6.1	Adverse events of special or potential interest of durvalumab - list of preferred terms	AS9	X
Table 14.3.6.2	Number of subjects with adverse events of special or potential interest of durvalumab by system organ class and preferred term (Safety)		X
Table 14.3.6.9	Adverse events of special or potential interest of durvalumab - Listing of key information (Safety)	TAE250	X
Table FDAAA1	Non-serious adverse events occurring in greater than 5% of subjects (Safety)	FDAAA1	(FDA)
Table 14.3.7.1.1	Clinical chemistry, coagulation and hematology laboratory variables over time (Safety)	S25(lab)	X
Table 14.3.7.1.2	Clinical chemistry, coagulation and hematology laboratory variables, CTCAE grade change from baseline to maximum on treatment (Safety)	TLAB020	X

TFL number	Title	Template	Abbreviated CSR

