Table 14.3.7.1.3	Clinically important changes in clinical chemistry, coagulation and hematology laboratory variables parameters (Safety)	TLAB060	X
Table 14.3.7.1.4	Proportion of subjects with elevated liver test based on measured laboratory values (Safety)	AS15	X
Table 14.3.7.1.5	Subjects with potential Hy's Law – individual subject data (Safety)	S32	X
Table 14.3.7.2	Clinical chemistry, coagulation and hematology laboratory variables, treatment-emergent changes outside local reference range – key subject information (Safety)	S28	X
Table 14.3.8.1	Vital signs variables, over time (Safety)	S25(vital)	X
Table 14.3.8.2	Vital signs variables, treatment-emergent changes outside predefined criteria – key subject information (Safety)	S28	X
Table 14.3.8.3	ECG variables over time (Safety)	S25(ecg)	X
Table 14.3.8.4	ECG, baseline versus last observation on treatment (Safety)	S41(ecg)	X
Table 14.3.8.5	QTcF, QTcf intervals and QTcB, at any observation on treatment (Safety)	S35	X
Figure 14.2.2.1	Individual total AZD2811 blood concentration-time plots - Log scale (Pharmacokinetics)	PK1	X
Figure 14.2.2.2	Individual metabolite (AZ12102238) blood concentration-time plots – Log scale (Pharmacokinetics)	PK1	X

TFL number	Title	Template	Abbreviated CSR
Figure 14.2.2.3	Geomean +/- gSD total AZD2811 blood concentration-time plots – Log scale (Pharmacokinetics)	PK1	X
Figure 14.2.2.4	Geomean +/- gSD metabolite (AZ12102238) blood concentration-time plots – Log scale (Pharmacokinetics)	PK1	X
Figure 14.3.7.1	ALT versus total bilirubin, expressed as multiples of ULN (Safety)	S9	X
Figure 14.3.7.2	AST versus total bilirubin, expressed as multiples of ULN (Safety)	S9	X
Figure 14.3.7.3	Liver biochemistry test results over time – subjects with elevated ALT or AST, and elevated total bilirubin, at any time (Safety)	S10	X
Appendix 16.2.1	Discontinued subjects	APL01	X
Appendix 16.2.1	Subjects with important protocol deviations	APL03	X
Appendix 16.2.2	Subjects affected by the global/country situation	APL24	X
Appendix 16.2.3	Subjects affected by the global/country situation - details	APL25	X
Appendix 16.2.3.1	Subjects excluded from analysis set	APL04	X
Appendix 16.2.4.1	Demographic and baseline characteristics, Assigned to study intervention	APL06	X
Appendix 16.2.4.2.1	Radiotherapy prior to treatment and post treatment, Assigned to study intervention		X

TFL number	Title	Template	Abbreviated CSR

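### SAP 3.2.3.5 converts a percent-only reticulocyte result with the white cell count, although the percentage is a share of red cells

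*SAP*

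**What the plan says.** SAP 3.2.3.5 (Laboratory Data) first explains how the white-cell differential is presented. The percentage is described as "relative numbers of each type of WBC in relationship to the total WBC", and the absolute value is that percentage times total WBC. The next paragraph deals with counts that were not supplied. It names the five white-cell types together with reticulocytes and applies one formula to all six; the relevant words are "monocytes and reticulocytes) is not reported, it will be derived as the total white blood cell count multiplied by the differential percentage".

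Protocol 8.2.4, Table 18, defines the differential as "Full White Blood Cell Count Differential: Neutrophils, Lymphocytes, Monocytes, Eosinophils, Basophils". Reticulocytes and red blood cells are separate entries in that table. Footnote a is attached to both the differential and the reticulocytes, and reads: "Can be recorded as absolute counts or as percentages. Absolute counts will be calculated by data management if entered as percentage". It then asks for the total white cell count for this purpose.

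On use of the results, SAP 4.2.3.3 says that "hematology results and change from baseline will be summarized using descriptive statistics" at each scheduled time, and that all individual laboratory data are listed. Appendix A plans Table 14.3.7.1.1 ("Clinical chemistry, coagulation and hematology laboratory variables over time (Safety"), Table 14.3.7.2 ("hematology laboratory variables, treatment-emergent changes outside local reference range") and the listing in Appendix 16.2.8.2.

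**The concern.** Reticulocytes are immature red cells, and a reticulocyte percentage is a proportion of red cells. Multiplying it by the white cell count gives a number with no meaning. It is wrong by orders of magnitude, and it moves with the white cells instead of with red-cell production.

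The second feature matters in this trial. Protocol Table 6 lists neutropenia as an identified risk of AZD2811 and anemia as a potential one, and G-CSF is mandatory in every cycle with AZD2811. White counts will therefore move for reasons unrelated to reticulocytes, and the derived value would follow them. The abbreviated CSR is meant to report safety in full, and reticulocytes help to interpret anemia.

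**Working it through.** The plan states no figure to reproduce. The check is a comparison of the passages, followed by an illustration of size.

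**Does the rule fit reticulocytes?**

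- The SAP's percentage is defined for white-cell types relative to total WBC.
- Protocol Table 18 names five cell types in the differential, and reticulocytes are not among them.
- The SAP rule nevertheless names reticulocytes. No other section of either document gives a separate rule for them.

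**Can it be triggered?** Yes. Footnote a allows a reticulocyte result to be entered as a percentage without an absolute count. The documents do not say how many sites report this way.

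**Size of the error.** Let p be the reticulocyte percentage.

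- Rule as written: p/100 x WBC
- Red-cell rule: p/100 x RBC
- Ratio of the correct value to the rule's value: RBC/WBC, whatever p is

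The documents give no cell counts, so all values below are assumptions. RBC is put in the same units as WBC (4.5 x10^12/L = 4500 x10^9/L).

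| Assumed inputs | Rule as written (x10^9/L) | Red-cell rule (x10^9/L) | Ratio |
|---|---|---|---|
| 1%, WBC 7, RBC 4500 | 0.01 x 7 = 0.07 | 0.01 x 4500 = 45 | 4500/7 = 643 |
| 1.5%, WBC 6, RBC 4500 | 0.015 x 6 = 0.09 | 0.015 x 4500 = 67.5 | 4500/6 = 750 |

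Range of the ratio:

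- WBC 2 to 10 and RBC 3000 to 4500: from 3000/10 = 300 to 4500/2 = 2250.
- WBC 1 to 10 and RBC 3000 to 5500: from 3000/10 = 300 to 5500/1 = 5500.

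**False trend.** Hold reticulocytes at 1% and RBC at 4500, so the true count stays at 45. If WBC falls from 7 to 2, the derived count goes from 0.07 to 0.02, a fall of 1 - 2/7 = 71%.

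**Effect on a pooled mean, if reticulocytes are summarized by visit.** Suppose every subject's true count is 45 and a fraction f is percent-only. The mean is (1 - f) x 45 + f x 0.07:

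- f = 10%: 40.5
- f = 25%: 33.8
- f = 50%: 22.5

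SAP 4.1 presents visit data while at least 3 subjects have evaluable data. With three subjects and one percent-only result, the mean is (45 + 45 + 0.07)/3 = 30.0.

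**Where the value goes.**

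- It would appear in the individual laboratory listing, Appendix 16.2.8.2.
- It could enter Table 14.3.7.1.1.
- SAP 3.2.3.5 compares absolute values with the local reference range, so it would be flagged low only where the laboratory has an absolute range for reticulocytes.
- It could reach Table 14.3.7.2 mainly if a subject's reporting format changed during the study, because a baseline derived the same way would already be low.

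**Where it does not go.** The SAP's hematology subset for change from baseline and CTCAE shifts is haemoglobin, WBC, ANC and platelets. Reticulocytes are also absent from the DLT criteria (protocol 4.1.3) and from the hematologic dose rules in protocol Table 21.

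**The case against.** The wording error is hard to dispute; the case on the other side is about reach.

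- **Summary tables.** Neither document says that reticulocytes are in Table 14.3.7.1.1. Change from baseline is limited to a subset that excludes them, and only the individual listing clearly contains them. This stands in part: SAP 4.2.3.3 can also be read as summarizing all hematology results, so the point is open.
- **Assumed numbers.** The cell counts and the percent-only fractions are not in the documents. Only 9 patients received AZD2811 with durvalumab, so 10% and 25% are not attainable fractions of that whole group. This stands; the pooled means are illustrations only. The factor RBC/WBC does not depend on them.
- **Source of the error.** Footnote a already ties the conversion to the white cell count and assigns it to data management. If data management fills the value first, the SAP sentence may never operate, and editing it alone may change nothing. This stands, and it is why the data-management specification must be corrected as well.
- **Consequence.** The study is descriptive, and no dose decision or efficacy result uses reticulocytes. This stands and sets the severity.

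**Conclusion.** The rule is wrong as written. Any reticulocyte count derived under it is too low by RBC/WBC: 643-fold at the assumed typical values, and 300- to 2250-fold over WBC 2 to 10 x10^9/L and RBC 3.0 to 4.5 x10^12/L. That the multiplier is wrong does not depend on these assumptions; the size does. How many results are affected cannot be known from the documents, and if every laboratory supplies absolute counts, none are. The severity is minor: individual listings are affected wherever the rule is used, the visit summary and range flags possibly, and ANC and efficacy not at all.

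**What to change.** Delete reticulocytes from the WBC-based sentence in SAP 3.2.3.5 and from the corresponding data-management specification. Add: absolute reticulocytes = reticulocyte percentage/100 x red blood cell count from the same sample; if RBC is missing, leave the absolute count missing and list the percentage only. Because footnote a of protocol Table 18 points to the white cell count, a line in SAP Section 6 (changes from protocol) would record the difference.

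The cost is a sentence in the SAP, a line in the data-management specification and, if wanted, the Section 6 entry. RBC is already collected under Table 18, so no new data are needed. Footnote a can be aligned if the protocol is revised for another reason; this point alone does not require an amendment.
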